Rationale: Bipolar disorder is a severe, chronic mental illness with currently limited treatment options, both cognitive behavioural therapy (CBT) and pharmacological treatment have modest effects. There is consensus for the need to improve effectiveness of cognitive behavioural therapy (CBT) for patients suffering from bipolar disorders. As for many other mental disorders specific treatments have been improved using imagery, and imagery appears to play a causal role in mood variability in bipolar disorders, adding imagery interventions to CBT might aid this aim. This feasibility study elaborates on a pilot study by Holmes (Holmes et al., 2016) and an audit (Hales et al., 2018) by comparing a new imagery enhanced cognitive behavioural therapy (ImCT) to psychoeducation treatment to evaluate the effectiveness of ImCT with an aim to inform a large planned RCT evaluating ImCT.

Objective: This study aims to evaluate the effectiveness of a new imagery enhanced cognitive behavioural therapy (ImCT) for patients suffering from bipolar disorders, by comparing ImCT to psychoeducation, one of the most regularly applied psychological interventions for bipolar disorder.

Study design: This study is a randomised feasibility trial, comparing ImCT intervention to psychoeducation. In addition to the between group design, we will also use a within-group design where ImCT or psychoeducation is preceded by and compared to baseline condition.

Study population: Patients between 18 and 68 years old, suffering from bipolar disorders, in care at a specialised centre for bipolar disorders (Centrum Bipolair) from a large psychiatric hospital (GGzE), having regular contact with their psychiatrist on medication advice.

Intervention: One group receives a new imagery enhanced cognitive behavioural therapy (ImCT), successfully piloted in a case series design in previous research (Holmes et al., 2016). The other group receives psychoeducation treatment. Both interventions consist of 12 hours active treatment and both interventions are carried out conform existing protocols. During the course of the study both groups keep receiving their regular consultation with a psychiatrist (to advise, monitor and if necessary adjust) for mood stabilising medication.

Main study parameters/endpoints: The primary outcome variable is changes in mood variability. The secondary outcome variables are changes in levels of depression, mania, anxiety, general level of functioning and level of hopelessness, number of relapses into mania and depression and changes in imagery characteristics.

Nature and extent of the burden and risks associated with participation, benefit and group relatedness: Risks for patients participating in this study are minimal. ImCT intervention has been successfully tested in a pilot study (Holmes et al., 2016) and an audit (Hales et al., 2018), suggesting this intervention is able to decline mood variability in patients suffering from bipolar disorder, and is also well tolerated and well received by patients. The

psychoeducation intervention closely resembles care as usual but is during this study delivered more structured by using a protocol. All patients, during the baseline period, during both treatments and during the follow-up period have regular appointments with their psychiatrist, who prescribes, monitors and adjusts mood stabilising medication. Should patients relapse into mania or depression, they will receive standard care as usual. Both interventions, ImCT and psychoeducation treatment are carried out conform existing protocols. The extra burden for patients, is the weekly questionnaires (20 minutes), and the questionnaires at T0-T4 (45 minutes), as daily mood monitoring is advised in current guidelines and part of care as usual.

1. INTRODUCTION AND RATIONALE

The DSM 5 defines bipolar disorder as a chronic and severe condition characterised by episodes of extreme moods, mania (or hypomania) and depression (Association, 2013). Bipolar disorder afflicts 1.9% to 2.4% of the general population (Regeer et al., 2004; ten Have, Bijl, & Nolen, 2002). In addition, bipolar disorder is associated with high inter episode distress and with ongoing mood swings (mood variability), high suicide risk, and high co-morbidity with other mental health problems especially anxiety (McElroy et al., 2001; Simon et al., 2004). Current interventions consist of pharmacotherapy and psychological interventions, predominantly psycho-education and cognitive behaviour therapy (CBT). Despite these interventions, 50% of patients do not recover within one year, only 25% achieve full recovery (Leahy, 2007), and 60% relapse again within two years (Geddes & Miklowitz, 2013). There is a consensus for the need to update CBT interventions and increase its effectiveness, aiming at not only managing symptoms, but also at targeting perpetuating or precipitating factors.

In a recent experimental study, O'Donnell and colleagues (O'Donnell, Di Simplicio, Brown, Holmes, & Burnett Heyes, 2017) showed that mental imagery might play a causal role in mood changes in patients suffering from bipolar disorders. Their findings are in line with ideas of Holmes and colleagues, proposing that mental imagery can act as an "emotional amplifier", thus driving mood changes (Holmes, Coughtrey, & Connor, 2008; Ng, Di Simplicio, & Holmes, 2016). Furthermore, experimental research showed that imagery has a greater effect on emotion (Holmes & Mathews, 2005; Holmes, Mathews, Dalgleish, & Mackintosh, 2006) and behaviour (Libby, Shaeffer, Eibach, & Slemmer, 2007) than verbal cognitions.

Mental imagery is considered a transdiagnostic feature of mental disorders (DiSimplicio et al., 2016; Holmes, Arntz, & Smucker, 2007) and added imagery interventions, enhanced the effectiveness of several cognitive behavioural interventions. For example updating appraisals of imagery has helped improve effectiveness of CBT for social phobia (Wild & Clark, 2011), targeting vividness of imagery during exposure and EMDR helped improve CBT treatment in patients suffering from PTSD (Ehlers, Clark, Hackmann, McManus, & Fennell, 2005). These findings suggest that adding imagery interventions might also improve CBT for bipolar disorder.

In 2016 Holmes and colleagues (Holmes et al., 2016) introduced a brief imagery-based cognitive intervention (ImCT) for patients suffering from bipolar disorder, using techniques aimed at both, quality of the imagery and appraisals of the imagery. ImCT is a promising intervention as it allows for flexible fine-tuning to target specific elements of imagery. ImCT incorporates an elaborate micro-formulation of imagery (teasing out both

qualitative aspects of imagery as well as appraisals), followed by metacognitive intervention, imagery rescripting or positive imagery and competing task (or a combination of these), tailoring the intervention depending on the outcome of the micro formulation. Holmes and colleagues (Holmes et al., 2016) conducted a pilot study using a non-concurrent baseline design, with a series of A-B replication. Fourteen patients with bipolar disorder were randomly assigned to 4, 5, or 6 weeks baseline after which they received ImCT (in total 10 to 14 sessions). Outcome measures were weekly measures of mood (mania, depression, and anxiety) and changes in targeted imagery. In addition, daily mood measures were collected using a smart phone text messaging to accurately measure mood variability. Result showed that patients reported an increase in mood stability, as well as improvements on weekly, and pre- and post-measures of mood and target imagery. Moreover, it is important to note that this study concluded that daily measurements were feasible. All in all, ImCT appears promising for bipolar disorder and invites further evaluation.

In the present research proposal, we elaborate on the previous ImCT pilot study (Holmes et al., 2016), comparing its effectiveness in patients with bipolar disorder to psychoeducation treatment. As noted before psychoeducation treatment is one of the most regularly applied psychological intervention for bipolar disorder. In advance of a large upcoming RCT in the UK it is necessary to derive more precise estimates of retention rates, especially on daily monitoring, and information on general feasibility as well as first data comparing ImCT to an appropriate control condition. We propose a randomised controlled feasibility study, comparing the effects of ImCT to psychoeducation in patients suffering from bipolar disorder in patients who standard have regular appointments with their psychiatrist, prescribing, monitoring and adjusting mood stabilising medication in a specialized bipolar treatment centre.

2. OBJECTIVES

Primary Objective and secondary objectives:

The present research project elaborates on a pilot study by Holmes and colleagues (2016) and an audit (Hales et al., 2018) using a new cognitive behavioural therapy enhanced with imagery techniques (ImCT), with an aim to improve the effectiveness of CBT for patients suffering from bipolar disorder. The pilot study (Holmes et al., 2016) found promising treatment effects but a controlled feasibility study is needed to test whether this treatment is more effective than regular treatment. Therefore, this research projects examines the effect of this new ImCT treatment, by comparing this intervention to psychoeducation treatment, one of the most regularly applied psychological intervention for bipolar disorder. The current

study will provide new insights for an upcoming large RCT evaluating the effectiveness of ImCT in the UK.

[figure not shown]
Our primary objective is to estimate the effects of ImCT compared to psychoeducation on mood variability. We hypothesise that (1) mood variability (primary outcome variable) will show stronger decreases in BD patients receiving ImCT at end of the intervention (T2), at follow-up measurement 8 weeks after concluding the interventions (T3) and at follow-up measurement 16 weeks after concluding the interventions (T4) than psychoeducation. Additionally, the effects of both treatments separately are also compared to baseline period preceding both treatments.

Our secondary objective is to estimate the effect of ImCT compared to psychoeducation on 1) level of depression, mania and anxiety and 2) general functioning and level of hopelessness (secondary outcome variables), 3) number of relapses into mania or depression and 4) changes in imagery characteristics. We hypothesise that (2a) symptoms of depression, mania and anxiety decrease and (2b) general functioning increase and level of hopelessness decrease (secondary outcome variables) more strongly in BD patients receiving ImCT than psychoeducation at T2, T3 and T4. Additionally, the effects of both treatments separately are also compared to baseline period preceding both treatments. We also hypothesise that 3) number of relapses into mania or depression after the end of ImCT are lower in the ImCT condition during the follow up period (T4) than in the psychoeducation condition. Finally, we hypothesises that 4) imagery characteristics will change more and problematic imagery decreases in the BD patients receiving ImCT at T2, T3 and T4, compared to baseline.

Note that, our primary outcome variable, mood variability, is measured in two ways. First, at baseline (T0), pre-intervention (T1), T2, T3 and T4. Second, mood variability is measured daily, during the four weeks baseline, during the intervention, and during the follow-up period (in total 16 weeks post intervention), in both the ImCT and psychoeducation conditions. Further note that the secondary outcome variables (2a), level of depression, mania and anxiety, are measured weekly throughout the duration of the study in both conditions and the secondary outcome variables (2b) general functioning and level of hopelessness and (4) changes in imagery are only measured at T0, T1, T2, T3 and T4. All measures are administered using an online secure server called Research Manager.

3. STUDY DESIGN

The present research proposal concerns a randomised feasibility trial, comparing ImCT intervention to psychoeducation. In addition to the between group design, the study also uses a within-group design, where ImCT and psychoeducation is preceded by a four-week baseline condition. Note that during this baseline period and throughout the study, all patients will maintain their regular appointments with their psychiatrist or specialised nurse practitioner, who will prescribe, monitor and adjust mood stabilising medication conform guidelines. The within-group design allows participants baselines to act as their individual control periods with no intervention (Barlow, Nock, & Hersen, 2009; Bonsall, Wallace-Hadrill, Geddes, Goodwin, & Holmes, 2012; Holmes et al., 2016). The study will take place within a specialised centre for bipolar disorders within a large psychiatric hospital (GGzE). All participants start after 4 weeks of baseline with either ImCT or psychoeducation treatment. The duration of the study for participants will be 32 weeks for participants in the ImCT condition and 26 weeks for participants in the psycho-education condition. The difference in duration between the conditions is due to treatment length, that is, 12 weeks weekly 1-hour sessions for ImCT and 6 weeks weekly 2-hour sessions for the psychoeducation treatment. Note that all participants will have had 12 hours face-to-face contact in both conditions.

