- Level of anxiety, using the Beck Anxiety Inventory (BAI) (Osman, Barrios, Aukes, Osman, & Markway, 1993). The BAI is a 21-item self-report questionnaire used for measuring the severity of anxiety. Answers are rated on a 4-point Likert scale (0-3). This is administered weekly throughout the duration of the study.
- Level of general functioning and coping: Participants rate their level of functioning using the Longitudinal Interval Follow up Evaluation – Range of Impaired Functioning Tool (Leon et al., 1999). This is a brief scale for people suffering from affective disorders, measuring four different functional areas (employment, interpersonal relations, satisfaction and recreation) on a 5-point Likert scale (low rating implies higher functioning). This is administered at T0, T1, T2, T3 and T4.
- Level of hopelessness: participants rate their hopelessness using the Beck Hopelessness Scale (Beck, Brown, & Steer, 1997), The BHS is a 20 item self-report scale measuring three aspects of hopelessness: feelings about the future, motivation and expectations. The BHS demonstrates good internal consistency (alpha = .93) and has high reliability in psychiatric samples (Beck et al., 1997). The BHS is administered at T0, T1, T2, T3 and T4.
- To assess number of relapses into mania and depression, scores on the above measures (ASRM for mania and QIDS-SR for depression) are used. Scores on the ASRM of 5 or more indicate a relapse into mania, a score of 10 or more on the QIDS a relapse into depression. This is measured using the weekly scores on the ASRM and QIDS-SR during the weekly measures in the follow up period (until 16 weeks after the end of either ImCT or psychoeducation).

To assess if (4) problematic imagery the following measures will be used:

- The Visual Analogue Scales of Imagery Characteristics (VAS-Imagery) have been tailored to BD populations. The scales range from 0-9. Examples are "How real / vivid / absorbing / preoccupying / compelling have your image(s) been over the past week"; "To which extent could you understand the role that the image(s) play in your mood instability?"; "To which extent could you find positive / helpful way of using the image(s)?" Target imagery is measured weekly throughout the duration of the study. Imagery characteristics are measured weekly throughout the duration of the study in both ImCT and psychoeducation treatment conditions.

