6.3.2 Study Assessment Moments

Psychoeducation groups at Centrum Bipolar start once in every six weeks. At four weeks prior to the start of each psychoeducation group the identified participants start with the online measures at baseline (T0), and both daily and weekly online measurements which participants receive by email. Note here that the patients that participate in this study will not wait longer than the patients that choose not to participate. Participants continue to fill in both the daily and weekly online measures for four weeks (the baseline period). After four weeks all participants fill in the measures pre-intervention (T1), and are allocated randomly to either the ImCT or psychoeducation condition, which will then commence. During the intervention period (12 weeks for the ImCT condition, and 6 weeks for the psychoeducation treatment condition) all participants continue to fill in both the daily and weekly online measures. At the end of the intervention, all participants fill in the post-intervention measures (T2) online. Subsequently, all participants continue to fill in both daily and weekly online measures until the end of the study (at follow up at 16 weeks). In addition, participants fill in the post-intervention online measures at follow up at 8 weeks (T3) and 16 weeks (T4) after the end of intervention.

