8. STATISTICAL ANALYSIS

First, descriptive analyses will be used to establish mean scores, standard deviations and to identify outliers. Missing data from our primary outcome variable, will be listwise deleted. In our other outcome variables, data will only be included if pre- and post-measures are completed.

Second, the data will be checked with respect to violation of assumptions (such as error independency, non-normal distributions) for variance-based models.

Primary outcome variable: mood variability:

To assess if there is a stronger decrease in mood variability in the ImCT intervention condition as compared to the psychoeducation condition, multivariate repeated measures analyses are applied. Dependent variables are the scores on the ALS-18 (baseline, T0; pre-treatment, T1; post-treatment, T2; 8-weeks follow-up, T3; 16-weeks follow-up, T4) with treatment condition (ImCT, psychoeducation) as between subjects variable.

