To assess if (2a) level of depression, mania and anxiety, (2b) general functioning and coping, and hopelessness increase/decline more in the ImCT intervention compared to psychoeducation treatment two types of multivariate repeated measures analyses are applied, both with treatment condition (ImCT, psychoeducation treatment) as independent, between groups variable. In the first type of analyses, the dependent variables are the scores of the weekly measures for depression, anxiety and mania (QIDS-SR, BAI, ASRM). In the second type of analyses, time (T0, T1, T2, T3 and T4) is used as within between subject variables and scores of the same instruments and general functioning and coping and hopelessness (ALS-18, IFE-RIFT, BHS) are used as dependent variables.

To assess if (3) number of relapse into mania or depression decline more in the ImCT intervention compared to psychoeducation treatment Chi-square analyses are applied with as dependent variable number of relapses into mania or depression, using cut-of scores on the ASRM and QIDS-SR during the follow-up period and treatment condition (ImCT, psychoeducation treatment) as between groups variable.

To assess if (4) problematic imagery decreases and imagery characteristics changes more by using the ImCT intervention compared to psychoeducation treatment, comparable to 2a and 2b, two types of multivariate repeated measures analyses are applied, both with treatment condition (ImCT, psychoeducation treatment) as between groups variable. In the first type of analyses, the dependent variables are the scores of the weekly measures of imagery (VAS). In the second type of analyses, time (T0, T1, T2, T3 and T4) is used as within between subject variables and scores of imagery (MICQ-BD and DIS) are used as dependent variables.

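### T2, T3 and T4 fall six weeks later after randomisation in ImCT than in psychoeducation, no arm comparison at equal elapsed time is planned, and the weekly models have no stated time axis

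*Combined protocol and SAP*

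**What the plan says.** Section 3 sets the duration at "32 weeks for participants in the ImCT condition and 26 weeks for participants in the psycho-education condition" and attributes the difference to treatment length, with 12 contact hours in each arm. Section 6.3.2 places randomisation at T1, after the four-week baseline, with treatment following directly. Treatment lasts "12 weeks for the ImCT condition, and 6 weeks for the psychoeducation treatment condition". T2 is the end of that treatment, and T3 and T4 come 8 and 16 weeks later.

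The aim in section 2 is estimation: "Our primary objective is to estimate the effects of ImCT compared to psychoeducation on mood variability". The hypothesis uses the same anchoring, for example "at follow-up measurement 8 weeks after concluding the interventions (T3".

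Section 8 analyses the primary outcome by visit label: "Dependent variables are the scores on the ALS-18 (baseline, T0; pre-treatment, T1; post-treatment, T2; 8-weeks follow-up, T3; 16-weeks follow-up, T4", with condition as the between-subjects factor. For the weekly symptom scales it says: "In the first type of analyses, the dependent variables are the scores of the weekly measures for depression, anxiety and mania (QIDS-SR, BAI, ASRM". It gives no week origin, window or number of weeks. A second analysis of the secondary outcomes uses T0 to T4. Apart from the primary outcome, section 8 admits data only where pre- and post-measures are both complete.

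On imagery, section 2 says "4) changes in imagery are only measured at T0, T1, T2, T3 and T4". Section 6.1.2 says "Imagery characteristics are measured weekly throughout the duration of the study in both ImCT and psychoeducation treatment conditions", and section 8 models a weekly imagery VAS.

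**The concern.** There are two separate issues.

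First, when the arms are compared at T2, ImCT patients have had 12 weeks since randomisation and psychoeducation patients 6. All patients continue psychiatric consultation with medication adjusted as needed (sections 3 and 5.2), and for some this consultation starts only at baseline. If mood variability drifts for reasons unrelated to the allocated treatment, six weeks of that drift enter the arm difference. Improvement over time would favour ImCT; worsening would count against it. The trial is meant to give estimates to a larger RCT, so a biased estimate matters even without a false significance claim.

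Second, a multivariate repeated-measures model needs the same occasions in both arms. The weekly series differ in length and no alignment is stated, so the time axis would be chosen at analysis.

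**Working it through.** **Schedule (sections 3 and 6.3.2).** The stated durations reproduce as baseline + treatment + follow-up: ImCT 4 + 12 + 16 = 32 weeks; psychoeducation 4 + 6 + 16 = 26 weeks.

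Weeks since randomisation:

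| Visit | ImCT | Psychoeducation | Gap |
|---|---|---|---|
| T2 | 12 | 6 | 6 |
| T3 | 12 + 8 = 20 | 6 + 8 = 14 | 6 |
| T4 | 12 + 16 = 28 | 6 + 16 = 22 | 6 |

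**Possible bias at T2 (illustration).** Assume the same linear drift in both arms and an ALS-18 SD of 11 (the SDs in Table 1, section 4.4, run from 10.49 to 12.74). Bias in d = 6 × slope / 11.

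- Slope from Table 1: end of treatment 35.54 to 24-week follow-up 34.71, taken as 24 weeks apart. (35.54 − 34.71) / 24 = 0.035 points per week. Bias = 6 × 0.035 / 11 = 0.02. These were treated pilot patients; the documents give no untreated drift rate.
- Assumed slope of 0.225 points per week: 6 × 0.225 = 1.35 points, and 1.35 / 11 = 0.12. The planned difference is 0.6 × 11 = 6.6 points, so this is 1.35 / 6.6 = 20% of it.
- Worsening at the assumed rate would shrink a true 0.6 to 0.6 − 0.12 = 0.48.
- If change levels off by week 12, T3 and T4 are unbiased, because both arms are then past that week.

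**Effect on significance claims.** Section 8 requires a significant omnibus test and then Bonferroni-corrected post hoc tests. This was simulated with 45 per arm, five visits, between-visit correlation 0.5, equal treatments, correction over T2 to T4 and 6,000 runs. At 0.225 points per week the omnibus arm-by-time test rejects in 9.0% (5.0% without drift). Omnibus and T2 are both significant in 1.1% (0.3% without drift).

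**Matched-time contrast from existing visits.** Interpolate psychoeducation between its own visits: 0.25 × 6 + 0.75 × 14 = 12, and 0.25 × 14 + 0.75 × 22 = 20. These match ImCT T2 and T3.

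- Standard error of the anchored contrast: 11 × √(2/45) = 2.32 points.
- Standard error of the matched contrast: 11 × √((1.625 + 0.375r)/45) = 2.16, 2.21 and 2.25 points for between-visit correlation r = 0.3, 0.5 and 0.7.
- If drift stopped abruptly at week 12, psychoeducation would have moved 6 and 12 weeks' worth at its T2 and T3. The interpolated value is 0.25 × 6 + 0.75 × 12 = 10.5 weeks' worth, leaving 1.5 × 0.225 / 11 = 0.03.

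**Weekly series.** From T0 there are nominally 32 weeks in ImCT and 26 in psychoeducation, so weeks 27 to 32 have no psychoeducation scores. From randomisation the lengths are 12 + 16 = 28 and 6 + 16 = 22, so weeks 23 to 28 have none. A complete-case model on every week drops the whole psychoeducation arm under either origin. Aligned to end of treatment, the 16 follow-up weeks match, but the treatment periods (12 and 6 weeks) do not.

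**The case against.** The strongest reply is that the anchoring is deliberate: it is disclosed, explained and identical to the hypothesis. That stands. The anchored contrast is a legitimate primary comparison, and nothing here contradicts it.

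The plan also offers a partial check. Section 8 includes within-arm tests between time points, so the psychoeducation change from T2 to T3 (weeks 6 to 14) would show how far controls move over the weeks at issue. This also stands, but it is not an arm comparison at equal elapsed time.

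A reader might infer that the offset invalidates the primary result or seriously inflates false claims. The documents do not support that. Their only slope gives a negligible bias, and the gated procedure keeps false T2 claims rare at the assumed slope. A steeper drift such as 0.45 points per week would mean 0.45 × 22 = 9.9 points, or 0.90 SD, in psychoeducation by T4. The pilot's whole change with ImCT, pre-treatment to 24-week follow-up, was 46.36 − 34.71 = 11.65 points. Even 0.225, if it ran linearly to week 22, implies 4.95 points (0.45 SD).

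A reader might also infer that hypothesis 2a cannot be tested. It can: the T0 to T4 analysis is aligned by visit, and a weekly model restricted to a common window could be fitted. The defect is that no window is stated.

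**Conclusion.** Both parts hold in limited form. The six-week offset at T2, T3 and T4 is exact. It is a disclosed design choice, and what is missing is a statement that the contrasts are not matched on time since randomisation, together with a matched-time sensitivity analysis. Any bias is of unknown size and direction: d = 0.02 at the pilot's post-treatment slope and 0.12 at an assumed 0.225 points per week, given equal linear drift in both arms and SD 11. The risk is mainly to the estimate, and the sample size calculation is unaffected.

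The weekly models are under-specified as written, and on all weeks a complete-case multivariate version cannot be fitted for both arms. The imagery discrepancy is a minor wording point. These changes should be made before analysis; confidence in the practical importance of the offset is moderate.

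**What to change.** 1. **Weekly QIDS-SR, ASRM and BAI.** Replace the multivariate model with one linear mixed model per outcome, with arm-specific curves in weeks since randomisation, a pre-specified curve form and covariance, and all available scores. State that this replaces section 8's pre-and-post completeness rule for these outcomes. Report contrasts at 0, 8 and 16 weeks after end of treatment as main (ImCT weeks 12, 20, 28 against psychoeducation 6, 14, 22). Report contrasts at common weeks since randomisation, up to week 22, as sensitivity. Note that in weeks 7 to 12 ImCT is still on treatment while psychoeducation is in follow-up.
2. **ALS-18.** Keep the anchored contrasts as primary and state that they are not matched on time since randomisation. Add a sensitivity analysis at week 12 (ImCT T2 against 0.25 × T2 + 0.75 × T3 of psychoeducation) and week 20 (ImCT T3 against 0.25 × T3 + 0.75 × T4).
3. **Imagery.** Reconcile section 2 (T0 to T4 only) with sections 6.1.2 and 8 (weekly VAS) before extending item 1 to the VAS.
4. **Relapse.** Leave this analysis on its equal 16-week post-treatment window.

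**Cost.** Analysis work and wording only, with no new visits or forms and similar precision. The matched-time contrasts assume a smooth trend between psychoeducation visits. Psychoeducation is then 6 and 14 weeks past treatment, so a departure from the primary result may reflect drift or a fading psychoeducation effect, and this analysis cannot tell which. ImCT week 28 has no concurrent control.
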